- Dose regimen: tusamitamab ravtansine will be administered on Day 1 as 100 mg/m² given via IV infusion and repeated Q2W. The duration of 1 cycle will be 14 days (1 administration of tusamitamab ravtansine per cycle). For participants with a body surface area (BSA) >2.20 m², the dose will be calculated based on a BSA of 2.20 m².

Noninvestigational medicinal products (NIMP)

Premedication with histamine H1 antagonist (diphenhydramine 50 mg or equivalent [eg, dexchlorpheniramine] given approximately 15 minutes [IV] to 1 hour [oral] before tusamitamab ravtansine administration) is required for all participants before administration of tusamitamab ravtansine. After first study intervention of SAR408701, patients should be observed for acute reactions at site up to 4 hours depending on any sign of drug-induced allergic reaction. Detailed instructions for dilution and administration of the IMP are provided in Pharmacy Manual. If a participant has experienced an infusion reaction in a previous tusamitamab ravtansine administration, premedication will also include dexamethasone 10 mg IV for future infusions. If the case participant does not experience any hypersensitivity reactions after 4 cycles, the premedication can be discontinued at the discretion of the Investigator.

Posttrial access to study medication: Not applicable.

Duration of study intervention

The expected duration of study intervention for participants may vary, based on disease progression date; median expected duration of study per participant is estimated as 40 weeks (up to 4 weeks for screening, a median of 24 weeks for treatment, and a median of 12 weeks for end of treatment assessments and the safety follow-up visit.

Statistical considerations:

- Sample size calculations:
 - Assuming a pre-screening failure rate of 84% and a study screening failure rate of 15%, approximately 285 participants will be pre-screened to achieve approximately 38 treated participants in the study. The initial plan is to treat a total of 38 participants evaluable for anti-tumor activity (at least 1 postbaseline tumor assessment, early clinical progression, or death due to disease progression).
- Main analysis population:
 - All-treated population: All enrolled participants exposed to the study treatment, regardless of the amount of treatment administered. All safety analyses will be

performed on this population, which is also the primary population for analysis of all efficacy parameters.

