Microcystic keratopathy/Keratitis	 Nonclinical: Mitotic arrest/single cell necrosis in the cornea of the eye in mice and monkeys. In addition, brown discoloration of the cornea associated, microscopically, with minimal dark pigmentation in cornea epithelial cells in monkeys. Findings considered related to the cytotoxic properties of DM4. Clinical: Reversible non-inflammatory, microcystic keratopathy/keratitis. Main dose-limiting toxicity (DLT) in the dose escalation part of study TED13751. Observations in the different phases of the clinical trial showed nonserious, mild to moderate AEs, no Grade 4-5 AEs were reported. The corneal TEAEs were manageable and reversible. Corneal TEAEs appeared: In TED13751 study in 30.1% of patients (56/186) in the pool of patients at 100 mg/m² Q2W, 32.1% of patients (9/28) in the Loading dose cohort, and 40.0% of patients (6/15) in the Dose Escalation Q3W phase. In TCD15054, in 50% of patients in the main dose escalation (3/6 patients) and in 50% of patients in the loading dose (8/16 patients). Regarding the ongoing studies ACT16525, ACT16146, ACT16432, EFC15858 among the patients treated there was no serious TEAE of keratopathy/keratitis. 	Careful collection of medical history and physical examination. Assessment of ocular/visual symptoms at each visit before IMP administration. Specific ocular tests at screening, whenever clinically indicated and at EOT. Wearing of contact lenses is forbidden. Preventive instillation of artificial tears or hyaluronic ophthalmic gel drops. Curative action: dose delay and reduction; artificial tears, corticosteroid eye drops and symptomatic treatment; ophthalmologist follow-up.

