6 STUDY INTERVENTION(S) AND CONCOMITANT THERAPY

Study intervention is defined as any investigational intervention(s), marketed product(s), placebo, or medical device(s) intended to be administered to a study participant according to the study protocol.

Using an infusion-controlled pump, tusamitamab ravtansine will be administered by IV infusion over 1 hour 30 minutes.

Prior to dosing, each participant's dose will be individually prepared by the study pharmacist or delegate and labeled with protocol number, participant number and treatment description.

One Day 1 of each treatment cycle, the patient's BSA will be determined using the current weight and baseline height. For patients with a BSA >2.20 m², the dose will be calculated on the basis of 2.20 m² BSA. After first administration of tusamitamab ravtansine, patients should be observed for acute reactions at site up to 4 days depending on any sign of drug allergic reaction.

Detailed instructions for dilution and administration of the IMP are provided in the Pharmacy Manual.

Intervention label	Tusamitamab ravtansine
Intervention name	Tusamitamab ravtansine
Intervention description	Tusamitamab ravtansine, Intravenous infusion 100 mg/m² Day 1 every 2 weeks
Туре	Drug
Dose formulation	Concentrate for solution for Intravenous (IV) infusion
Unit dose strength(s)	5 mg/mL
	125 mg/25 mL
Dosage level(s)	Tusamitamab ravtansine Intravenous (IV) infusion 100 mg/m² Day 1 every 2 weeks
Route of administration	Intravenous infusion
Use	experimental
IMP and NIMP	IMP

Table 4 - Study intervention(s) administered

STUDY INTERVENTION(S) ADMINISTERED

Packaging and labeling	Tusamitamab ravtansine is supplied in a 30 mL type I glass vial. Each IMP kit contains 1 vial of 125 mg/25 mL of tusamitamab ravtansine labeled with a multilingual booklet. The content of the labeling at vial and box level is in accordance with the local regulatory specifications and requirements.
	regulatory specifications and requirements
Current/former name(s) or alias(es)	Tusamitamab ravtansine

Abbreviations: IMP = investigational medicinal product; NIMP = noninvestigational medicinal product

Arm title Tusamitamab ravtansine Arm type Experimental Arm description Participants will receive intravenous (IV) administration 100 mg/m² every 2 weeks (Q2W) Associated intervention labels Not applicable

Table 5 - Study arm(s)

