6.5 DOSE MODIFICATION

Dose adjustment and/or cycle delay are permitted in case of adverse reaction. In case of toxicity, cycle delays and dose modifications should be implemented according to the Appendix 6 (Section 10.6). Every effort will be made to administer the full dose regimen and maximize dose intensity.

Dose adjustments will be made according to the worst grade of adverse reaction observed within a cycle. If a participant experiences several adverse reactions and there are conflicting recommendations, the most conservative dose adjustment recommended should be followed.

Administration of the study treatment will be discontinued in the event of a TEAE that persists despite appropriate dose modifications or any other AE that, in the opinion of the Investigator, warrants discontinuation.

Dose modifications different from those stated in the protocol should only be made in consultation with the Sponsor unless required for immediate participant safety.

All changes to study treatment administration must be recorded in the electronic CRF (eCRF).

The acceptable treatment window for tusamitamab ravtansine administrations is 2 days.

One dose reduction is allowed for safety reason. Dose delay is allowed for safety management. Retreatment of patients that require more than one-month dose delay need to be justified with case by case risk benefit assessment. See Table 10 in Appendix 6 (Section 10.6) for guidance in dose modification or discontinuation. During the conduct of the study, second dose reduction may be needed, and need to be decided on a case by case basis following discussion with the sponsor.

If a dose reduction is necessary, the study intervention will be administered as follows:

Drug name	Dose	Reduced dose
Tusamitamab ravtansine	100 mg/m ² Q2W	80 mg/m² Q2W

Table 6 - Individual tusamitamab ravtansine dose reduction

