	Grade 3-4 eg, symptomatic bronchospasm, urticaria lesions covering >30% BSA, hypotension, angioedema.	Interrupt SAR408701 infusion and definitively discontinue SAR408701.	Give diphenhydramine 50 mg IV and/or dexamethasone 10 mg IV and/or epinephrine and any required treatment per Investigator judgment.
Ocular toxicity: Keratopathy/keratitis ^b associated with SAR408701	Grade 1 Asymptomatic, Corneal lesions only observed on routine ocular examination and not requiring topical treatment.	Next infusion of SAR408701 at the same dose, with or without cycle delay, depending on the recommendation from the ophthalmologist (nature and extent of the lesion).	Standard ocular examination is planned as recommended by the ophthalmologist.

Table 10 - Recommended Dose Modification or Discontinuation for SAR40870

Event	Symptoms severity (NCI-CTCAE v5.0)	Dose modification	Supportive care guidelines
	Grade 2 Symptomatic, moderate decrease in visual acuity (best corrected visual acuity 20/40 and better or 3 lines or less decreased vision from known baseline)	1 st episode: SAR408701 cycle delay until resolution to Grade 1 (asymptomatic) and restart SAR408701 at the same dose. 2 nd episode: delay cycle until resolution to Grade 1 (asymptomatic) and SAR408701 dose reduction.	Standard ocular examination weekly until resolution ^{c} . Start curative treatment per ophthalmologist recommendation. After resuming study treatment, participant should be followed with standard ocular examination by every 2 cycles, even asymptomatic during next four cycles. If no recurrence, standard process with follow-up with ocular symptom is resumed. Management of study drug and follow-up process upon recurrence
	Grade 3 Symptomatic with marked decrease in visual acuity (best corrected visual acuity worse than 20/40 or more than 3 lines of decreased vision from known baseline, up to 20/200); corneal ulcer; limiting self-care ADL.	1 st episode: SAR408701 cycle delay until resolution (asymptomatic) and restart SAR408701 with dose reduction. 2 nd episode: definitive discontinuation of SAR408701.	to be discussed according to Grade of the event at recurrence, clinical benefit from study drug and recommendation from the ophthalmologist.

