Febrile neutropenia	Grade 3 Absolute neutrophil count <1000/mm ³ with a single temperature of >38.3°C (101°F) or a sustained temperature of \geq 38°C (100.4°F) for more than 1 hour	Delay cycle until ANC >1500/mm ³ . 1st episode: administer next cycle at the same dose and administer G-CSF 2nd episode: administer SAR408701 at reduced dose 3rd episode: definitive discontinuation	To ensure relative dose intensity, G-CSF is recommended as secondary prophylaxis in all participants with Grade ≥3 febrile neutropenia ASCO guideline is recommended for supportive treatment if there are no defined clinical standards (20).
	Grade 4 Life-threatening consequences	Administration changes to be decided at the Investigator's discretion. 1st episode: administer next cycle at reduced dose and administer G-CSF or definitively discontinue 2nd episode: definitive discontinuation	
Hepatic enzyme increase	Grade 1-2	Administer SAR408701 as planned.	No intervention.
	Grade 3	Delay the cycle. Restart the treatment until recovery to Grade 1.	Additional liver function tests will be done every 2-3 days until recovery to baseline value.
	Grade 4	SAR408701 should be permanently discontinued.	Additional liver function tests will be done every 2-3 days until recovery to baseline value.
Peripheral neuropathy	Grade 1 Asymptomatic	No action	Participant who has ongoing grade 1 neuropathy has high risk of

Clinical Trial Protocol SAR408701-ACT17241 - tusamitamab ravtansine 27-Sep-2021 Version number: 1

Event	Symptoms severity (NCI-CTCAE v5.0)	Dose modification	Supportive care guidelines
	Grade 2 Moderate symptoms; limiting instrumental Activities of Daily Living	Delay cycle, dose reduction if no improvement with dose delay	worsening of his/her symptoms and should be closely followed.
	Grade 3 Severe symptoms; limiting self-care Activities of Daily Living	Definitive discontinuation	-
	Grade 4 Life-threatening consequences; urgent	Definitive discontinuation	-

ASCO = American Society of Clinical Oncology; BSA = Body surface area; ECG = Electrocardiogram; G-CSF = Granulocyte colony-stimulating factor; IMP = Investigational medicinal product; IV = Intravenous; LLN = Lower limit of normal; LVEF = Left ventricular ejection fraction; NCI-CTCAE = National Cancer Institute Common Terminology Criteria for Adverse Events; and RBC = Red blood cell.

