3.6.1 Extent of exposure

The dose information will be assessed by the following:

- Number of cycles started per participant.
- Duration of exposure (in weeks) is defined by (date of last administration of the IMP + 14 days date of first administration of the IMP)/7.
- Actual dose (in mg/m²). In case of dose interruption, actual dose will be the sum of the actual doses administered before and after the dose interruption.
- Cumulative dose (in mg/m²): the cumulative dose is the sum of all actual doses of tusamitamab ravtansine, given from first to last administration
- Actual dose intensity (ADI in mg/m²/week): defined as the cumulative dose divided by the duration of tusamitamab ravtansine exposure (in weeks)

- Planned dose intensity (PDI in mg/m²/week): corresponds to the planned dose at C1D1 + planned dose at subsequent cycles multiplied by the theoretical total number of doses started 1 and divided by the theoretical cycle duration expressed in weeks (ie, 2 weeks per cycle started)
- Relative dose intensity (RDI, in %):100 × ADI ([mg/m²/week])/PDI ([mg/m²/week])

The total number of cycles started, number of cycles started by participant will be summarized as a quantitative variable and by category (number [%] of participants receiving at least 1 cycle, at least 2 cycles, etc). Duration of tusamitamab ravtansine exposure, cumulative dose, ADI and RDI will be summarized quantitatively.

The following variables will be derived to describe dose modifications and dose interruptions:

• Dose reduction: The first administration (loading dose) and second administration (first 100 mg/m² infusion) will not be counted as a dose reduction. For the third and subsequent tusamitamab ravtansine administrations, dose reduction will be determined using the dose level intervals provided in Table 6, by comparing the current dose level to the previous dose level. If the current dose level is below the dose level interval of the previous dose administration, then the current dose Table 6 level is considered reduced.

Actual dose level	Dose level interval
Starting dose (100 mg/m² Q2W)	>90 mg/m²
Dose level -1 (80 mg/m² Q2W)	>72.5 mg/m² and ≤90 mg/m²
Low dose	>0 mg/m² and ≤72.5 mg/m²

Table 6 - Tusamitamab ravtansine dose reduction criteria

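### SAP 3.6.1 exempts the second administration from dose-reduction counting on a loading-dose premise that this trial does not have, so a reduction first made there and then held is never counted

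*SAP*

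**What the plan says.** **The counting rule.** SAP 3.6.1 sets this exemption: "The first administration (loading dose) and second administration (first 100 mg/m² infusion) will not be counted as a dose reduction". From the third administration on, a reduction is flagged when the dose level falls below the interval of the previous administration. The intervals are above 90 mg/m², above 72.5 and up to 90 mg/m², and 72.5 mg/m² or less. The table that defines them begins with "Starting dose (100 mg/m² Q2W") and has no loading level.

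**The regimen.** The protocol synopsis says "tusamitamab ravtansine will be administered on Day 1 as 100 mg/m² given via IV infusion and repeated Q2W". Protocol Table 4 says "Tusamitamab ravtansine, Intravenous infusion 100 mg/m² Day 1 every 2 weeks". Protocol 4.1 and SAP 1.1 give the same single regimen. Elsewhere in the documents a loading dose belongs only to cohorts of other studies, as in Protocol Table 1: "32.1% of patients (9/28) in the Loading dose cohort".

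**Reductions at the second administration.** Protocol 6.5 says "Dose adjustments will be made according to the worst grade of adverse reaction observed within a cycle". In Protocol Table 10 (Appendix 6), a first episode of Grade 3 keratopathy leads to "cycle delay until resolution (asymptomatic) and restart SAR408701 with dose reduction". For Grade 4 febrile neutropenia the table says "1st episode: administer next cycle at reduced dose and administer G-CSF or definitively discontinue". Retreatment is subject to the Day 1 criteria in Protocol 6.5.1.

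**Where the definition is used.** SAP 3.6.1 reports participants and cycles with at least one dose reduction. SAP 3.7.1.1 drops trough concentrations after a delay or reduction as defined in 3.6.1, and drops end-of-infusion and end-of-infusion + 1 h concentrations after a reduction.

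**The concern.** The rule would make sense where the first dose is a loading dose and the drop to 100 mg/m² at the second administration is planned. Here both doses are planned at 100 mg/m², so any drop at the second administration is a real reduction. The exemption hides it. Because later doses are compared only with their predecessor, the hidden step is not picked up afterwards unless the dose falls again.

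At stake is a descriptive tolerability result. The reductions missed are the earliest ones, made after a single dose. Cycle delay, by contrast, is left undefined only for the first cycle and so is assessed from the second. The PK summaries inherit the same gap.

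**Working it through.** **Inputs.** The dose bands, the exemption and the comparison rule come from SAP 3.6.1. The reduced dose of 80 mg/m² is from Protocol Table 6. The planned 38 treated participants and the 20 at the interim are from Protocol 9.3 and 9.4. The dose sequences are illustrations, not predictions.

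**Step 1: apply the rule.** A reduction is counted at administration *k* if its band is lower than the band at *k* − 1. The SAP starts at *k* = 3; the alternative starts at *k* = 2.

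| Sequence (mg/m²) | SAP rule | From administration 2 |
|---|---|---|
| 100, 80, stop | 0 | 1 |
| 100, 80, 80, 80 | 0 | 1 |
| 100, 80, 100, 100 | 0 | 1 |
| 100, 100, 80, 80 | 1 | 1 |
| 100, 80, 80, 60, 60, 60 | 1 | 2 |

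In the second row, administration 2 is exempt, and administration 3 (80 against 80) shows no drop. In the last row a further fall is counted, so that participant still enters the row for at least one reduction, but the first step is lost.

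**Step 2: size per missed participant.**
- 1/38 = 2.6 percentage points.
- 1/20 = 5.0 percentage points, if enrollment stops at the interim.
- The cycle row loses one cycle for each such participant.

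The documents give no rate of reductions at the second administration, so no total can be calculated.

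**Step 3: what an accompanying delay changes.** A cycle counts as delayed when it starts more than 2 days after the planned 14, that is, more than 14 + 2 = 16 days after the first dose.
- With such a delay, as is likely under the keratopathy row, the participant still appears in the delay and dose-modification rows. The delay already excludes the troughs that the reduction would have excluded.
- Without it, the dose-modification rows and the trough exclusion are wrong too.

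**Step 4: PK samples.** The end-of-infusion + 1 h exclusion depends on reduction alone, so that sample stays in whether or not there was a delay. Its cycle label is broken in the text available; it lies between Cycles 2 and 4 and is read here as Cycle 3. The number of troughs wrongly kept in the no-delay case depends on whether the SAP means only the next trough or every later one.

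**Step 5: what does not change.** Relative dose intensity uses the actual doses. With on-time dosing it is 340/400 = 85% for 100/80/80/80 and 180/200 = 90% for 100/80, under either counting rule.

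**The case against.** The strongest reply is that this is a leftover sentence in an untested descriptive summary, with limited reach. Much of that stands.

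- **The routes are narrow.** Protocol 6.5.1 requires neutrophils of at least 1.5 × 10⁹/L and, apart from alopecia, no IMP-related toxicity above Grade 1 or baseline severity. After Grade 4 febrile neutropenia in Cycle 1, meeting this within 16 days is possible but demanding. Protocol Table 1 describes corneal events so far as mild to moderate. The routes remain open, however.
- **Grade 2 neuropathy.** A reader might add this as a third route, since Table 10 provides for reduction when a delay brings no improvement. Unimproved Grade 2 toxicity conflicts with 6.5.1 read literally, so the point does not rely on it. Those two places need to be reconciled.
- **Other outputs show part of the picture.** Reductions made for an adverse event fall under the SAP Table 5 summary of events leading to dose modification, though mixed with delays. Action taken is tabulated for corneal events. Cumulative dose and relative dose intensity also fall. None of these corrects the reduction rows or the PK exclusions.

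A reader might try to size the undercount from the 3.3% serious Grade 3–4 febrile neutropenia in EFC15858. The documents do not support that: the figure covers both grades, is not confined to Cycle 1, and the table gives no dose or arm for it.

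**Conclusion.** The rule is wrong as written for this trial. Its premise contradicts the regimen in both documents and the SAP's own dose-level table, and it returns 0 where a participant has had one held reduction from the second administration. The error is 2.6 points per missed participant if 38 are treated, or 5.0 if 20. The number missed is unknown and may be zero, so severity is minor.

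A reader might infer that efficacy or dose intensity is also at risk. It is not: ORR, the futility rule, the sample size, actual dose intensity and relative dose intensity do not use the reduction variable.

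A reader might also link this to the body surface area constant in SAP 5.4.1, which reads 0.0007184 in the text available. That is a separate query to check against the source file. The text was machine-read, so it cannot be treated as an error in the plan, and it forms no part of this conclusion.

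**What to change.** In SAP 3.6.1, delete the loading-dose sentence and state that dose reduction is assessed from the second administration onward, against the dose level of the previous administration. The PK exclusions in SAP 3.7.1.1 then follow through their use of the definition. It would help to say there whether the trough exclusion covers only the next trough or all later ones.

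The cost is SAP wording and programming. No data collection, dose or clinical rule changes.

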3.6.2 Adverse events

General common rules for adverse events

All AEs will be graded according to the National Cancer Institute Common Terminology for Adverse Events (NCI-CTCAE version 5.0) and coded to a lower-level term (LLT), preferred term (PT), high-level term (HLT), high-level group term (HLGT), and associated primary system organ class (SOC) using the Medical Dictionary for Regulatory Activities (MedDRA) version in effect at Sanofi at the time of database lock.

The AEs will be analyzed in the following 3 categories:

- Pre-treatment AEs: AEs that developed, worsened or became serious during the pre-treatment period.
- Treatment-emergent adverse events (TEAE)s: AEs that developed, worsened or became serious during the treatment-emergent period.
- Post-treatment AEs: AEs that developed, worsened or became serious during the post-treatment period.

Similarly, deaths will be analyzed in the pre-treatment, treatment-emergent and post-treatment periods.

The primary AE analyses will be on TEAEs. Pre-treatment and post-treatment AEs will be described separately.

An AE with incomplete or missing date/time of onset (occurrence, worsening, or becoming serious) will be classified as a TEAE unless there is definitive information to determine it is a pre-treatment or a post-treatment AE.

If the assessment of the relationship to IMP is missing for an AE, this AE will be assumed as related to IMP. Missing grade will be left as missing.

Multiple occurrences of the same event in the same participant will be counted only once in the tables within a treatment phase, using the maximum (worst) grade by treatment phase. Summaries will be provided for all grades combined and for grade ≥ 3 (including grade 5). Missing grades, if any, will be included in the "All Grades" category.

The AE tables will be sorted as indicated in Table 4.

Table 4 - Sorting of AE tables		
AE presentation	Sorting rules	
SOC, HLGT, HLT and PT	By the internationally agreed SOC order and by alphabetic order of HLGTs, HLTs and PTs.	
SOC and PT	By the internationally agreed SOC order and decreasing frequency of PTs ^{a, b}	
[SMQ/CMQ] and PT	By decreasing frequency of SMQs/CMQs and PTs ^a	
PT	By decreasing frequency of PTs ^a	

Sorting will be based on the SAR408701 group incidence. а

The table of all TEAEs presented by primary SOC and PT will define the presentation order for all other tables (eq, treatment-emergent b SAEs) presented by SOC and PT, unless otherwise specified.

Analysis of all adverse events

The overview of TEAEs with the details below will be generated:

- Any TEAE •
- Any grade ≥ 3 TEAE
- Any treatment-emergent SAE
- Grade 5 TEAE (any TEAE with a fatal outcome during the treatment-emergent period)
- Any treatment-emergent AESI
- Any TEAE leading to permanent intervention discontinuation
- Any TEAE related to IMP
- Any Grade \geq 3 TEAE related to IMP
- Any treatment-emergent SAE related to IMP
- Any treatment-emergent corneal event (CMQ "Corneal events compound level")
- Any treatment-emergent peripheral neuropathy event (SMQ "Peripheral neuropathy" [Narrow and Broad])
- Any ocular/visual symptoms TEAE (CMQ "Eye disorders exclude corneal disorders" ie, • all PTs included in "Eye disorders" [SOC] excluding PTs in SMQ "Corneal disorders" [Narrow]")

The AE summaries of Table 5 will be generated with number (%) of participants experiencing at least one event. The analyses will be performed for all grades combined and for grades ≥ 3 .

Type of AE	MedDRA levels
All TEAE	Primary SOC, HLGT, HLT and PT
	Primary SOC and PT
	PT
TEAE related to IMP as per Investigator's judgment	Primary SOC and PT
Treatment emergent SAE	Primary SOC, HLGT, HLT and PT
	Primary SOC and PT
Treatment emergent SAE related to IMP as per Investigator's judgment	Primary SOC and PT
TEAE leading to permanent intervention discontinuation	Primary SOC and PT
TEAE leading to death ^b	Primary SOC and PT
AE leading to death ^b	Primary SOC and PT
- In context of disease progression ^c	
- In context other than disease progression ^d	
	Primary SOC and PT
Pretreatment AE	Overview ^a
	Primary SOC and PT
Pretreatment SAE	Primary SOC and PT
Post-treatment AE	Overview ^a
	Primary SOC and PT
Post-treatment SAE	Primary SOC and PT
TEAE leading to dose modification (including dose delay and dose reduction)	Primary SOC and PT
TEAE leading to dose interruption	Primary SOC and PT

Table 5 - Analyses of adverse events

a Will include the following AE categories: any AEs, any serious AEs, any AEs leading to death, any AEs leading to permanent intervention discontinuation

b Death as an outcome of the AE as reported by the Investigator in the AE page

c Death within 30 days from last IMP administration and the cause of death is disease progression

d Death within 30 days from last IMP administration and for whom cause of death is not disease progression or the death occurred more than 30 days from last IMP administration and the cause of death is AE

Analysis of deaths

In addition to the analyses of deaths included in Table 4, the number (%) of participants in the following categories will be provided:

• Deaths during the treatment-emergent and post-treatment periods by study period and main reason for death

- An overview of Grade 5 AEs will be provided with the following categories:
 - Grade 5 AE (TEAE and post-treatment).
 - Fatal TEAE (regardless of date of death/period).
 - Grade 5 TEAE with a fatal outcome during the treatment-emergent period,
 - Any Grade TEAE with a fatal outcome during the post-treatment period.
 - Post-treatment Grade 5 AE (excluding a TEAE that worsened to Grade 5 during the post-treatment period).

In addition, a listing of deaths in non-enrolled participants or enrolled but not treated participants will be provided on the prescreened population.

Analysis of adverse events of special interest (AESIs) and other AEs of interest

Adverse events of special interest (AESIs) and other AEs of interest will be selected for analyses as indicated in Table 6. Number (%) of participants experiencing at least one event will be provided, by SOC and PT if applicable. Tables will be sorted as indicated in Table 4.

AESIs and other AEs of interest	Selection	
AESIs		
Grade ≥3 keratopathy/keratitis	e-CRF AESI specific tick box on the AE page. It could include Grade ≥3 events with PTs from CMQ of corneal events	
Bundle branch blocks or any conduction defects.	e-CRF AESI specific tick box on the AE page. It could include events with PTs from SMQ "Conduction defects"	
Grade ≥3 liver enzyme increased (symptomatic or asymptomatic)	e-CRF AESI specific tick box on the AE page. It could include Grade ≥3 events with the following PTs: "Alanine aminotransferase increased", "Aspartate aminotransferase increased", "Transaminases increased", "Hepatic function abnormal", "Hepatic enzyme increased", "Liver function test increased", "Transaminases abnormal", "Hepatic enzyme abnormal", or "Liver function test abnormal"	
Symptomatic overdose (serious or nonserious) with IMP	e-CRF symptomatic overdose specific tick box on the Overdose page	
Pregnancy of a female participant entered in a study as well as pregnancy occurring in a female partner of a male participant entered in a study with IMP	eCRF specific tick box for adverse event linked to pregnancy on the Pregnancy page	
Other AEs of interest		
Corneal events	CMQ "Corneal events compound level" containing the PTs included in both SOC "Eye disorders" and SMQ "Corneal disorders" (Narrow)	
Ocular/visual adverse events (excluding corneal disorders)	CMQ "Eye disorders exclude corneal disorders" containing PTs included in SOC "Eyes disorders" and excluding PTs in SMQ "Corneal disorders" (Narrow)	
Cardiac conduction defects	SMQ "Conduction defects" (Narrow)	

Table 6 - Selections for AESIs and other AEs of interest
--

Property of the Sanofi group - strictly confidential

AESIs and other AEs of interest	Selection
Peripheral neuropathy events	SMQ "Peripheral neuropathy" (Narrow and Broad)
Colitis events (excluding infective)	CMQ "Colitis (excluding infective)" containing PTs included in HLT "Colitis (excl infective)"
Hypersensitivity events	SMQ "Hypersensitivity" (Narrow) and defined as events occurring on the day or the day after the infusion
Hepatic disorders adverse events	SMQ "Hepatic Disorders" (Narrow and Broad)
Hematological adverse events	SMQ "Haematopoietic cytopenias" (Narrow and Broad)
AE related to COVID-19 illness	SMQ "COVID-19" (Narrow)

An overview of corneal TEAE will be provided with the following AE categories: any corneal TEAE, Grade \geq 3 corneal TEAE, treatment-emergent corneal SAE, corneal TEAE related to IMP, Grade \geq 3 corneal TEAE related to IMP, corneal TEAE leading to treatment discontinuation, and corneal TEAE leading to dose modification (cycle delay or dose reduction). In addition, a summary table of corneal events will be displayed by grade. A summary of treatment-emergent corneal events will be provided.

- Cycle of first onset of corneal event regardless of the grade
- Cycle of first onset of corneal event with the worst grade
- Number (%) of participants by worst grade
- Relationship to the study intervention: in case of multiple events with different relationships, if any event is related, then the relationship will be considered as related
- Action taken with the study intervention: in case of multiple events with different actions, the most severe action taken will be tabulated and selected according to the following order of severity: drug withdrawn, dose reduced and delayed, dose reduced, dose delayed, drug interrupted, dose not changed
- Outcome: in case of multiple events with different outcomes, the most severe outcome will be tabulated and selected according to the following order of severity: fatal, not recovered or resolved, recovering or resolving, recovered or resolved with sequelae, recovered or resolved, unknown

In addition, analyses on occurrence and recurrence of corneal events will be provided. An occurrence of corneal event is defined as one or a group of concomitant corneal events. A recurrence is defined as any new occurrence of corneal event starting after a previous resolved occurrence.

- The number of occurrences by participant
- The time to first onset of corneal event will be described using Kaplan-Meier curves. Time to first onset is defined as the time from the date of first IMP administration to the date of the first occurrence of the event. In the absence of an event before the analysis cut-off date, it will be censored at the end date of the treatment-emergent period, analysis cut-off date or date of death, whichever occurs first.

- The time to recovery will be summarized using descriptive statistics in participants who had had at least one recovered or resolved occurrence of corneal event (with or without sequelae), considering the longest duration among all occurrences by participant.
- The time to recurrence will be summarized using descriptive statistics in participants who had had at least one recurrence, considering the shortest time among all recurrences by participant.

Besides the AE categorized as ocular/visual adverse events, all ocular/visual symptoms (coded term) recorded in e-CRF as associated symptom of the reported ocular treatment-emergent adverse events will be reported as descriptive analysis. Same analysis will be done separately for ocular/visual symptoms associated to corneal TEAEs (CMQ)."

